5. POTENTIAL RISKS AND CHARACTERISTICS

5.1 Exercise:

There is the possibility of muscle soreness and injury from the exercise training program. The muscle soreness may last several days after the testing and after each exercise training session, but it is not likely to be severe enough to limit any usual daily activities. There is also a risk of muscle injury from the exercise training program. Muscle injuries may require medical attention, may take several months to heal, and may limit usual daily activities for a period of days, weeks, or months. It is expected that all study participants will incur at least minor muscle soreness over the course of the entire intervention.

5.2 DXA scan:

The cumulative radiation exposure from this test is considered small and is not likely to adversely affect disease status.

5.3 D3-creatine dilution test:

There are no known risks.

5.4 Blood draw:

Local pain, bruising, and, in rare instances, an infection might occur at the site where blood is drawn. There is also the possibility of dizziness or fainting while blood is being drawn.

6. ADVERSE EVENTS

6.1 Chemotherapy toxicity

As differences in chemotherapy-associated toxicities are part of objectives of the study, chemotherapy-associated toxicities will be monitored and recorded throughout chemotherapy period. However, severity and grading will not require reporting to IRB as those would be expected with standard of care treatment.

6.2 Adverse events and serious adverse events

Any unfavorable or unintended medical or psychological event experienced by a study participant during clinical research, sometimes referred to as an adverse experience or adverse effect. An AE can represent a new symptom or an exacerbation or worsening of an existing condition. It is not necessarily causally related to or associated with the investigational agent or protocol.

A serious adverse event (SAE) is any adverse event, occurring at any dose and regardless of causality that:

- Results in death
- Is life-threatening. Life-threatening means that the person was at immediate risk of death from the reaction as it occurred, i.e., it does not include a reaction which hypothetically might have caused death had it occurred in a more severe form.
- Requires or prolongs inpatient hospitalization (i.e., the event required at least a 24-hour hospitalization or prolonged a hospitalization beyond the expected length of stay). Hospitalization admissions and/or surgical operations scheduled to occur during the study period but planned prior to study entry are not considered SAEs if the illness or disease existed before the person was enrolled in the trial, provided that it did not deteriorate in an unexpected manner during the trial (e.g., surgery performed earlier than planned).
- Results in persistent or significant disability/incapacity. Disability is defined as a substantial disruption of a person's ability to conduct normal life functions.
- Is an important medical event when, based upon appropriate medical judgment, it may jeopardize the participant and require medical or surgical intervention to prevent one of the outcomes listed above.

Events **not** considered to be serious adverse events are hospitalizations for:

- Routine treatment or monitoring of the studied indication, not associated with any deterioration in condition, or for elective procedures;
- Elective or pre-planned treatment for a pre-existing condition that did not worsen;
- Emergency outpatient treatment for an event not fulfilling the serious criteria outlined above and not resulting in inpatient admission; and
- Respite care.

6.3 Expectedness

Adverse events can be 'Expected' or 'Unexpected.'

6.3.1 Expected adverse event:

Expected adverse events are those that have been previously identified as resulting from the intervention. For the purposes of this study, an adverse event is considered expected when it appears in the informed consent document as a potential risk.

6.3.2 Unanticipated problem (UP):

Any incident, experience, or outcome that meets **all** of the following reporting criteria:

- Unexpected (in terms of nature, severity, or frequency) given (a) the research procedures that are described in the protocol-related documents, such as the IRB-approved research protocol and informed consent document; and (b) the characteristics of the subject population being studied;
- Related or possibly related to participation in the research where *possibly related* means there is a reasonable possibility that the incident, experience, or outcome may have been caused by the procedures or interventions involved in the research); and
- Suggests that the research places subjects or others at a greater risk of harm (including physical, psychological, economic, or social harm) than was previously known or recognized.

PIs must report UPs involving risk to subjects or others to the IRB.

6.3.3 Attribution:

Attribution is the relationship between an adverse event or serious adverse event and the study intervention. Attribution will be assigned as follows:

- Definite – The AE is clearly related to the study intervention.
- Probable – The AE is likely related to the study intervention.
- Possible – The AE may be related to the study intervention.
- Unlikely - The AE is doubtfully related to the study intervention.
- Unrelated - The AE is clearly NOT related to the study intervention.

6.3.4 Procedures for AE and SAE recording and reporting:

- 6.3.4.1 The PI or designee will investigate and analyze any event or incident to determine whether it is reportable to the IRB.

To determine whether an event or incident is a reportable UP, the PI or designee must answer and comment on the following **three** questions:

1. Is the event or incident unexpected in nature, severity, or frequency?
Evaluate whether the event or incident is described as a risk in the research application, investigators' brochure, or informed consent document and outside the expected severity or frequency.
2. Is the event or incident related or possibly related to participation in the research?

Evaluate whether the event or incident could reasonably have been caused by participation in the research.

3. Does the unanticipated incident, experience, event, and/or outcome suggest, in the PI's opinion, that either:
 - a. The research places subjects or others at a greater risk (including physical, psychological, economic, or social harm) than was previously known or recognized; **or**
 - b. This incident has more than a minimal effect on the integrity of the study or research results?

Determination 1: If the answer to **all three questions** above is "Yes," the event or incident is a UP and must be reported to the IRB. See PI Reportable Event and Incident Requirements SOP KPNC-502 for timeframe to report upon discovery.

Determination 2: If any answer is "No," the event or incident is **not** a UP and does not have to be reported as a UP; **however**, analysis is required to determine if reporting should be made as a different type of reportable event or incident (e.g., noncompliance).

6.3.4.2 All AEs and SAEs whether reported by the participant, discovered during questioning, directly observed, or detected by physical examination, laboratory test or other means, will be recorded in the appropriate study-specific case report forms.

6.3.4.3 The descriptions and grading scales found in the revised NCI Common Terminology Criteria for Adverse Events (CTCAE) version 4.0 will be utilized for AE reporting. All appropriate treatment areas should have access to a copy of the CTCAE version 4.0. A copy of the CTCAE version 4.0 can be downloaded from the CTEP [website](#).

6.4 Reporting requirements:

6.4.1 Each participating investigator is required to abide by the reporting requirements set at their individual sites.

6.4.2 Each investigative site will be responsible to report SAEs that occur at that institution to their respective IRB. It is the responsibility of each participating investigator to report serious adverse events to the Kaiser overall principal investigator.

6.4.3 Serious adverse event reporting:

All serious adverse events that occur after the initiation of study intervention, during intervention or within 30 days after completion of intervention must be reported to the Kaiser Permanente overall principal investigator using the individual site's SAE form. This includes events meeting the criteria outlined in Section 6.2, as well as the following:

- Grade 3 (severe) Events – Only events that are unexpected and possibly, probably or definitely related/associated with the intervention.

- All Grade 4 (life-threatening or disabling) events – Unless expected AND specifically listed in the protocol as not requiring reporting.
- All Grade 5 (fatal) Events – When the participant is enrolled and actively participating in the trial OR when the event occurs within 30 days of the last study intervention.

Participating investigators must report each serious adverse event to the Kaiser Permanente Overall Principal Investigator within 24 business hours of learning of the occurrence. In the event that the participating investigator does not become aware of the serious adverse event immediately (e.g., participant sought treatment elsewhere), the participating investigator is to report the event within 24 business hours after learning of it and document the time of his or her first awareness of the adverse event. Report serious adverse events by telephone, email or facsimile to:

[name]
Division of Research
Kaiser Permanente
[name]
[name]
[contact]
[contact]

Within the following 24-48 hours, the participating investigator must provide follow-up information on the serious adverse event. Follow-up information should describe whether the event has resolved or continues, if and how the event was treated, and whether the participant will continue or discontinue study participation.

6.4.4 Reporting to the Institutional Review Board (IRB):

All unanticipated serious adverse events should be reported to the Kaiser Permanente IRB as defined by the PI Reportable Event and Incident Requirements SOP KPNC-502. Other investigative sites should report serious adverse events to their respective IRB according to the local IRB's policies and procedures in reporting adverse events.

6.4.5 Reporting to Hospital Risk Management:

Participating investigators will report to their local Risk Management office any subject safety reports or sentinel events that require reporting according to institutional policy.

7. CRITERIA FOR REMOVAL FROM STUDY

Patients will be removed from study when any of following criteria occur: new invasive cancer diagnosis or recurrence; decision of the participant to stop receiving chemotherapy treatment; request of the patient to withdraw; illness that prevents further administration of the intervention; or study team or treating clinicians deem continued participation not safe for patient. Patients who are removed from study will be asked to complete follow-up assessments if clinically feasible and patients are agreeable. Reason for removal from study will be recorded in patient's study record.

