2. OBJECTIVE

2.1 Primary Objective:

To examine differences in dose reductions, dose delays and early stoppage for chemotherapy and the total combined number of moderate and severe chemotherapy-associated toxicities between intervention group and waitlist controls.

2.2 Secondary Objectives:

2.2.1 Examine specific inflammatory markers (CRP, IL-6, TNF- α receptor II [TNF-RII]) in relation to baseline MM and FM and examine differences in changes in inflammatory markers between intervention group and waitlist controls.

2.2.2 Examine the impact of intervention versus control and RT-induced body composition changes on the pharmacokinetics [PK] of 5-FU and oxaliplatin between baseline and 4 months of RT.

2.3 d3 Creatine Objectives:

2.3.1 Test whether resistance training during chemotherapy (FORCE intervention group v. control) increases d3 creatine muscle mass at 6 months.

2.3.2 Evaluate the association of d3 creatine muscle mass with changes in functional status and strength during chemotherapy.

2.3.3 Evaluate the association of d3 creatine muscle mass with chemotherapy toxicity and relative dose intensity.

2.3.4 Evaluate the association of d3 creatine muscle mass with cancer-related biomarkers, including inflammation, CEA levels and cardiometabolic risk factors.

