9. STATISTICAL CONSIDERATIONS

9.1 Study design:

This randomized controlled trial of resistance training intervention in colon cancer patients receiving chemotherapy consists of two arms: an in-person and telephone-based intervention to promote home-based resistance training, and a wait-list, control group. After consent and baseline visit measurements, randomization assignment will utilize a covariate adaptive randomization procedure which ensures that equal numbers of patients are assigned to each study arm and that the two arms remain balanced on five key characteristics: site of participation [Kaiser Permanente vs Penn State vs Dana-Farber]; gender [male vs female]; cancer stage [stage II vs stage III], and duration of chemotherapy [3 months vs 6 months]; planned chemotherapy regimen [FOLFOX vs CAPOX vs capecitabine vs 5-FU/LV]. This randomization method (also known as the minimization method) has been demonstrated to outperform simple randomization or stratified randomization in terms of achieving balanced groups, particularly in smaller trials with multiple important prognostic factors.

The primary objective of this trial is to compare the effect of a RT intervention versus a wait-list control on chemotherapy dose reductions, dose delays, early discontinuation of chemotherapy and treatment-related toxicity. The secondary objective is to compare the effect of the intervention versus wait-list control on changes in inflammatory biomarkers, and the tertiary objective is to compare pre and post intervention pharmacokinetics of 5-FU and oxaliplatin. The d3 Creatine objective is to compare the effect of a RT intervention versus a wait-list control on d3 creatine muscle mass at 6 months.

9.2 Sample size, accrual time and study duration:

One hundred and eighty (180) participants will be recruited and randomized over a total of 3.5 years. Patient involvement and data collection will last approximately 6 months.

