9.2.1 From Section D. Study overview of the original KPNC application approved 2017

3. How many participants will be enrolled in this study, or how many electronic records or medical records will be used? Provide your best estimate if you are not sure

Number of KPNC participants or records:	Approximately 115 participants to be enrolled
Records used:	Approximately 7500-KPNC records used
Number of non-KPNC participants or records:	Approximately 65 participants enrolled
Total number of participants or records:	Approximately 180* participants enrolled

**Due to the impact of the COVID-19 pandemic on the study, we estimate that the total number of participants will be within the range of 10% above the original total of 180 participants*

9.3 Statistical analysis:

9.3.1 Primary endpoints:

All data analyses will be by intent-to-treat, though in exploratory analyses we will consider compliance to intervention (defined as $\geq 75\%$ of planned sessions) and changes in MM. We will use multiple linear regressions to assess the difference between the intervention and wait-list control groups in mean relative dose intensity (RDI) for each agent and in mean average RDI (ARDI) across all agents. Continuous model covariates will be categorized either as quartiles or into clinically relevant categories (e.g. WHO BMI classification).

Analysis of number of grade 3 and 4 toxicities in relation to randomization arm will utilize Poisson regression given that this outcome can be characterized as a count. These regression models will provide point and interval estimates of adjusted proportional differences in rates of toxicities (expressed as rate ratios) between the control and intervention groups.

9.3.2 Secondary endpoints:

Analyses of inflammatory markers in relation to baseline body composition will utilize multiple linear regression techniques. These analyses of associations at baseline will be conducted in each randomization arm separately, followed by an analysis in the full sample (differences in associations at baseline across arms are not expected).

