## **STATISTICAL CONSIDERATIONS**

### **2.1 Sample Size**

This study intended to randomize 180 colon cancer patients, with 90 in each treatment arm. In the end, due to missing data due to COVID, we randomized 183 participants, 92 to RT and 91 to UC. We expect chemotherapy dosing and completion rates (RDI, ARDI) to be assessed on all participants.

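### Removal from study for illness that stops the exercise programme can end PRO-CTCAE reporting in the resistance training arm, with no counterpart among controls

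*Protocol*

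**What the plan says.** Protocol Section 7 lists events on which a patient leaves the study, among them "decision of the participant to stop receiving chemotherapy treatment; request of the patient to withdraw; illness that prevents further administration of the intervention". The first and the last of these matter here. The section does not distinguish leaving the exercise programme from leaving data collection. What follows removal is covered by one sentence: "Patients who are removed from study will be asked to complete follow-up assessments if clinically feasible and patients are agreeable".

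The primary objective (Protocol 2.1) covers "dose reductions, dose delays and early stoppage for chemotherapy" together with chemotherapy toxicities. In the SAP the primary toxicity endpoint is the patient-reported PRO-CTCAE, completed around the start of each cycle (SAP 1.2).

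Collection of that questionnaire is described differently by arm. Under footnote 1 to Table 7 in Protocol Section 4, RT patients complete it at their intervention visits and only afterwards by phone or web-link for each chemotherapy appointment. Controls are reached by phone or web-link for every chemotherapy appointment from the start. Protocol 4.12 places the emailed web-link within the intervention period.

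On analysis, the protocol states "All data analyses will be by intent-to-treat" (9.3.1), and its power section (9.3.4) expects RDI and toxicity counts on the full sample. SAP 2.1 states "We expect chemotherapy dosing and completion rates (RDI, ARDI) to be assessed on all participants"; it does not name PRO-CTCAE.

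**The concern.** An illness that stops the intervention can be recorded only where there is an intervention to stop. Controls are told not to take up weight training (Protocol 3.10), so in practice the trigger belongs to RT. Such a patient may remain on chemotherapy for several cycles. If removal ends contact, those cycles yield no PRO-CTCAE report, while an equally ill control is still prompted at each appointment.

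The direction matters. SAP 2.2 analysis A asks whether any of 8 symptoms was ever moderate or severe. Analysis B counts how many of the 8 were so at least once. Neither makes a stated allowance for the number of cycles observed. A missing report can only leave these scores unchanged or lower them, so arm-specific loss favours RT. Analysis C works per cycle and does not fall mechanically with fewer reports, but it too would favour RT if the unreported cycles are the worse ones.

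**Working it through.** **1. The plan's own figure.** Protocol 9.3.4 gives 80% power for 0.42 SD, two-sided alpha 0.05, with no loss assumed for RDI or toxicity counts. At 90 per arm the noncentral t gives power 0.800, and 0.42 × 17.3 = 7.27, stated as 7.3 RDI points. With the 92 and 91 actually randomized, the detectable difference is 0.416 SD, or 7.2 points. The figure reproduces, but it rests on complete ascertainment. Losing 5%, 10% or 15% of 90 RT patients altogether would lower power only to 0.791, 0.778 or 0.764. Precision is not the difficulty; the one-sided loss is.

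**2. Analysis A.** The documents give no removal or symptom rates, so all inputs here are assumptions: chance p per cycle of any moderate or severe report, independent cycles, 12 planned cycles, no true effect, and a share f of RT patients with no reports after cycle 6.

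- risk(k) = 1 − (1 − p)^k
- observed RT risk = (1 − f) × risk(12) + f × risk(6)

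For p = 0.10: risk(12) = 1 − 0.9^12 = 0.718 and risk(6) = 1 − 0.9^6 = 0.469. With f = 0.10 the observed RT risk is 0.9 × 0.718 + 0.1 × 0.469 = 0.693. The odds ratio is (0.693/0.307)/(0.718/0.282) = 0.89.

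| p per cycle | risk(6) | risk(12) | OR, f = 5% | OR, f = 10% | OR, f = 15% |
|---|---|---|---|---|---|
| 0.05 | 0.265 | 0.460 | 0.96 | 0.92 | 0.89 |
| 0.10 | 0.469 | 0.718 | 0.94 | 0.89 | 0.84 |
| 0.20 | 0.738 | 0.931 | 0.87 | 0.76 | 0.68 |

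On the risk scale the effect is bounded. With x = (1 − p)^6, risk(12) − risk(6) = x − x², which cannot exceed 0.25. With f = 10% and a cut at cycle 6, the RT risk therefore falls by at most 0.10 × 0.25 = 2.5 percentage points. Patients with frequent symptoms will often have reported one before removal.

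**3. Analysis B.** If p is instead the per-cycle chance for each symptom, the spurious ratio of mean counts is 1 − f × (1 − risk(6)/risk(12)). For p = 0.10 and f = 0.10: 1 − 0.10 × (1 − 0.469/0.718) = 0.965.

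**4. A participant who chooses to stop chemotherapy.** There is no later cycle at which PRO-CTCAE is due, in either arm. For RDI, SAP 1.1 counts missed cycles, so stopping after 6 of 12 full-dose cycles scores about 6/12 = 50%. It would score 100% only if the record were cut at removal and the untreated cycles ignored, which the SAP does not prescribe.

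**5. RDI after removal for illness.** Doses come from the medical record (Protocol 4.11) and need no patient contact. The loose end is in SAP 1.1: the delivered-dose window runs from randomization to follow-up, and follow-up is not defined for a removed patient. If the window closed at removal, the direction of error would depend on the handling. Later delivered cycles treated as missed would lower RT's RDI; later dose reductions left out would raise it.

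**The case against.** The strongest reply is that the planners kept lost visits apart from primary data. Protocol 9.3.4 applies the 10% dropout to DXA and blood only and expects toxicity metrics on everyone; the analysis is by intent-to-treat; Section 7 does invite removed patients to follow-up. Footnote 1 to Table 7 ends by tying RT questionnaires to each chemotherapy appointment, which could be read as continuing after the exercise visits end. Part of the SAP and the appendix forms were not available, so a rule may exist there.

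Most of this stands for RDI. For PRO-CTCAE it does not settle the matter: an expectation of full data is not a procedure for obtaining it, the footnote does not mention removed patients, 4.12 places the web-link within the intervention period, and the SAP's all-participants sentence stops at RDI and average RDI.

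A reader might infer more than the documents support, in three ways.

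- That Section 7 truncates a primary outcome, since the trial also compares "early discontinuation of chemotherapy and treatment-related toxicity". The trigger is the participant's own decision, not every stop, and step 4 shows that such a stop does not by itself truncate RDI or PRO-CTCAE.
- That RDI is biased towards RT by the share removed times the RDI gap, for example 10% × 20 points = 2.0 against a 7.3-point target. That deletes whole patients, whereas the documents expect RDI on all of them.
- That Section 7 contradicts intent-to-treat. It does not say that collection or analysis ends; it leaves complete ascertainment unsecured.

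**Conclusion.** The point holds for PRO-CTCAE. As written, Section 7 allows toxicity reporting to end for RT patients who become too ill to train but continue chemotherapy, and no comparable route exists among controls. That the trigger is confined to RT is an inference from the control arm's content. Other removal criteria, such as withdrawal or unsafe participation, can apply in either arm.

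The loss would favour RT in analyses A and B. Its size cannot be known from the documents. Under the assumptions in step 2 the spurious odds ratio is about 0.89 (range 0.68 to 0.96), a shift of at most 2.5 percentage points in risk when 10% of the arm is cut at cycle 6. Independence between cycles is a simplification: persistent symptoms would mostly have been reported before removal, which makes the shift smaller. RDI needs only a defined end to its window.

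**What to change.** Reword Section 7 so that the listed events end the exercise intervention and not data collection. Unless the patient withdraws consent for data collection, medical-record abstraction of dosing and toxicity should run to the planned last cycle, and PRO-CTCAE prompts should continue at each remaining chemotherapy appointment, by the same route in both arms. SAP 1.1 should state that the RDI window does not close at removal.

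The SAP describes randomization and questionnaire completion in the past tense, so collection may be over and missed questionnaires may be unrecoverable. In that case: complete the record abstraction to the planned last cycle for all 183 patients; report removals by arm and reason, with the number of PRO-CTCAE cycles due and completed; and add a sensitivity analysis for the missing cycles in analyses A to C, ranging from each patient's own observed rate to all missing cycles being moderate or severe.

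The cost is small: protocol and SAP wording, some abstraction work and, if patients are still on treatment, a few more web-link questionnaires. The clinical criteria for stopping exercise or chemotherapy are not judged here and stay as they are.
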